## SOCIAL PROTOCOL (HRP-580)

PROTOCOL TITLE: App-Assisted Day Reconstruction to Reduce Treatment Burden and Logistic Toxicity in Cancer Patients – Aim 1  
 VERSION DATE: 01/05/2023

### ANCILLARY REVIEWS

**DO NOT DELETE.** Submit the completed checklist below with your protocol.

Which ancillary reviews do I need and when do I need them? Refer to HRP-309 for more information about these ancillary reviews.			
Select yes or no	Does your study...	If yes...	Impact on IRB Review
 Yes  No	Include Gillette resources, staff or locations	Gillette Scientific review and Gillette Research Administration approval is required. Contact: [contact]	Required prior to IRB submission
 Yes  No	Involve Epic, or Fairview patients, staff, locations, or resources?	The Fairview ancillary review will be assigned to your study by IRB staff Contact: [contact]	Approval must be received prior to IRB committee/designated review.
 Yes  No	Include evaluation of drugs, devices, biologics, tobacco, or dietary supplements or data subject to FDA inspection?	STOP – Complete the Medical Template Protocol (HRP-590)  The regulatory ancillary review will be assigned to your study by IRB staff Contact: [contact] See https://policy.umn.edu/research/indide	Consider seeking approval prior to IRB submission.
	Require Scientific Review? Not sure? See guidance in the Investigator Manual (HRP-103).	ONLY REQUIRED BIOMEDICAL RESEARCH REVIEWED BY FULL COMMITTEE	
 Yes  No	Relate to cancer patients, cancer treatments, cancer screening/prevention, or tobacco?	Complete the CPRC application process. Contact: [contact]	
 Yes  No	Include the use of radiation? (x-ray imaging, radiopharmaceuticals, external beam or brachytherapy)	Complete the AURPC Human Use Application and follow instructions on	Approval from these committees must be

## SOCIAL PROTOCOL (HRP-580)

PROTOCOL TITLE: App-Assisted Day Reconstruction to Reduce Treatment Burden and Logistic Toxicity in Cancer Patients – Aim 1  
 VERSION DATE: 01/05/2023

		the form for submission to the AURPC committee.  Contact: [contact]	received prior to IRB approval;  These groups each have their own application process.
 Yes   No	Use the Center for Magnetic Resonance Research (CMRR) or MR at Masonic Institute for the Developing Brain (MIDB) as a study location?	Complete the CMRR pre-IRB ancillary review  Contact: [contact]	
 Yes   No	Include the use of recombinant or synthetic nucleic acids, toxins, or infectious agents?	STOP – Complete the Medical Template Protocol (HRP-590)	
 Yes   No	Include the use of human fetal tissue, human embryos, or embryonic stem cells?	STOP – Complete the Medical Template Protocol (HRP-590)	
 Yes   No	Include PHI or are you requesting a HIPAA waiver?	If yes, HIPCO will conduct a review of this protocol.  Contact: [contact]	
 Yes   No	Use data from CTSI Best Practices Integrated Informatics Core (BPIC)  Formerly the AHC Information Exchange (AHC-IE)?	The Information Exchange ancillary review will be assigned to your study by IRB staff  Contact: [contact]	Approval must be received prior to IRB approval.  These groups do not have a separate application process but additional information from the study team
 Yes   No	Use the Biorepository and Laboratory Services to collect tissue for research?	STOP – Complete the Medical Template Protocol (HRP-590)  The BLS ancillary review will be assigned to your study by IRB staff.  Contact: [name] [contact]	
 Yes   No	Have a PI or study team member with a conflict of interest?	The Col ancillary review will be assigned to your study by IRB staff  Contact: [contact]	

**SOCIAL PROTOCOL (HRP-580)**

PROTOCOL TITLE: App-Assisted Day Reconstruction to Reduce Treatment Burden and Logistic Toxicity in Cancer Patients – Aim 1  
VERSION DATE: 01/05/2023

 Yes  No	Need to be registered on clinicaltrials.gov?	If you select "No" in ETHOS, the clinicaltrials.gov ancillary review will be assigned to your study by IRB staff Contact: [contact]	may be required.
 Yes  No	Require registration in OnCore?	If you select "No" or "I Don't Know" in ETHOS, the OnCore ancillary review will be assigned to your study by IRB staff Contact: [contact]	Does not affect IRB approval.

**SOCIAL PROTOCOL (HRP-580)**

**PROTOCOL TITLE:** App-Assisted Day Reconstruction to Reduce Treatment Burden and Logistic Toxicity in Cancer Patients – Aim 1  
**VERSION DATE:** 01/05/2023

**SOCIAL PROTOCOL (HRP-580)**

**PROTOCOL TITLE:** App-Assisted Day Reconstruction to Reduce Treatment Burden and Logistic Toxicity in Cancer Patients – Aim 1  
**VERSION DATE:** 01/05/2023

**REVISION HISTORY**

Revision #	Version Date	Summary of Changes	Consent Change?
1	07/27/2022	Clarify that study team may screen participants in the clinic and that participants may complete consent in-person as well (in addition to electronic consent).	N
2	08/09/2022	Remove Aims 2 and 3 from this protocol as those will be submitted to a commercial IRB separately due to conflict of interest concerns for those aims; this will be led by Daynamica	N
3	09/06/2022	Increase number to be consented from 20 to 30, goal remains the same to obtain interviews from 20 participants.	N
4	01/05/2023	Allow for follow-up survey to be completed online (original plan) or paper (new)	N

SOCIAL PROTOCOL (HRP-580)

PROTOCOL TITLE: App-Assisted Day Reconstruction to Reduce Treatment Burden and Logistic Toxicity in Cancer Patients – Aim 1

VERSION DATE: 01/05/2023

**SOCIAL PROTOCOL (HRP-580)**

**PROTOCOL TITLE:** App-Assisted Day Reconstruction to Reduce Treatment Burden and Logistic Toxicity in Cancer Patients – Aim 1  
**VERSION DATE:** 01/05/2023

**ABBREVIATIONS/DEFINITIONS**

AUC Area under the curve  
EHR Electronic Health Record  
CAB Community Advisory Board  
MARS Mobility App Rating Scale  
PETS Patient Experience with Treatment and Self-Management  
POI Point of interest  
TBQ Treatment Burden Questionnaire

## SOCIAL PROTOCOL (HRP-580)

PROTOCOL TITLE: App-Assisted Day Reconstruction to Reduce Treatment Burden and Logistic Toxicity in Cancer Patients – Aim 1

VERSION DATE: 01/05/2023

### 1.0 Objectives

1.1 Purpose: The number of new cases of cancer diagnosed in the U.S. was 1.7 million in 2017 and is expected to increase by 35% to 2.3 million in 2030[1]. Cancer treatments often create numerous logistic challenges in prioritizing and managing treatment and everyday life priorities and how these challenges affect their everyday lives and well-being (hence “logistic toxicity”). However, there are no established reliable tools to monitor patients’ logistic challenges and the associated impacts; and logistic toxicity has been largely unaddressed in cancer care delivery. Our objective is to develop the first **digital health app for cancer patients** to continuously monitor logistic toxicity in their daily lives. The app will combine **objective data** from mobile sensing with **subjective self-reported data** to form an app-assisted day reconstruction system that captures activity engagement and well-being information associated with cancer treatment-related activities and trips throughout the day.

The proposed patient monitoring app that captures logistic toxicity information on an ongoing basis will empower patients to advocate for care that better fits their life, give providers new insights into potential reasons for treatment non-adherence and nonresponse, and allow health systems to design more patient-centered care regimens.

We will use a participatory design approach to inform the design of our system, engaging an 8-member community advisory board (CAB; including 2 patients, 2 oncologists, 1 nurse, 1 patient advocate, 1 payer, and 1 hospital administrator), and performing in-depth interviews and follow-up surveys with 20 diverse patients undergoing treatment for cancer. Patients will supply examples of logistic toxicity and how they would like to measure and communicate logistic toxicity across scenarios. Follow-up surveys will ask participants to provide satisfaction ratings towards user interface sketches and app function narratives.

### 2.0 Background

2.1 Significance of Research Question/Purpose: Symptom burden and financial toxicity have been widely acknowledged side-effects of cancer, but logistic toxicity—the toxic effects of the logistic burden of carrying out cancer treatment tasks on patient well-being - has only recently received any attention.[2-7] Sources of logistic toxicity include scheduling and attending appointments, engagement with different care providers, pharmacy visits, consultations, insurance paperwork, managing drugs, transportation, and wait times. The well-being effects of these burdens can be biographical (loss of freedom, independence, and time availability to engage in meaningful activities), relational (strained family and social relations), and emotional (feelings of anger, anxiety, frustration, worry, and guilt).[8]

Logistical challenges in treatment burden can lead to poor treatment adherence, low quality of life, and worsening of disease; and it negatively affects family and

## SOCIAL PROTOCOL (HRP-580)

PROTOCOL TITLE: App-Assisted Day Reconstruction to Reduce Treatment Burden and Logistic Toxicity in Cancer Patients – Aim 1

VERSION DATE: 01/05/2023

friends, employers, and healthcare payers and providers.[9-15] Further, burdens of cancer and cancer treatments disproportionately affect disadvantaged patients such as racial and ethnic minorities, and hence logistic toxicity is likely to reinforce persistent inequities in cancer care and outcomes.[16-19]

The cancer care landscape has rapidly evolved to accommodate COVID-19 precautions, transitioning toward telehealth, greater emphasis on patient self-management, and opportunities for providers to tailor treatment plans. Oncology clinical practices can potentially adopt interventions such as minimally disruptive medicine, care coordination, and telemedicine that could reduce logistic toxicity in cancer care delivery.[20, 21] However, implementing these interventions requires tools that can reliably track patients' behavior and well-being in navigating the day-to-day logistic burden of undertaking cancer treatment tasks.

2.2 Preliminary Data: The concept of logistic toxicity in cancer care is similar to the concepts described in treatment burden in chronic disease management, Burden of Treatment Theory, and the Cumulative Complexity Model.[22, 23] Within these frameworks, instruments such as the Treatment Burden Questionnaire (TBQ) and the Patient Experience with Treatment and Self-management (PETS) have been developed to collect self-reported, recall-based data on treatment burden.[24, 25] Building upon this prior research, effective monitoring of logistic toxicity needs to capture the **objective treatment workload** (i.e., activities and trips carried out by the patient for treatment purposes) as well as the **subjective effects** of that workload on well-being (i.e., including biographical, relational, and emotional effects).[3-7] Objective measures of logistic toxicity to date have relied on electronic health records (EHR) and claims data, which cover medical and pharmacy visits only and offer limited information on other important sources of logistic toxicity such as scheduling time, transportation, and wait time. Subjective measures to date are research-oriented retrospective measurements that are not timely enough to inform or help the patient.

(1) Our app will offer a remote patient monitoring platform to capture logistic toxicity information on a timely and ongoing basis; 2) it will apply machine learning techniques to automatically infer cancer treatment-related activities and trips as a way to minimize the need for manual input, and 3) it will integrate objective mobile sensing with subjective patient input to generate more accurate and complete summaries of logistic toxicity.

On this project, we will collaborate with Daynamica Inc. In 2013-2015, Daynamica developed an app-assisted day reconstruction system that integrates smartphone sensing and surveying capabilities capturing spatiotemporal and other details of daily activities and trips, leading to a US Patent titled “Travel and Activity Capturing”.[26-27] The system was later augmented with experience sampling capabilities to capture well-being during the day. Since then, the Daynamica app has

## SOCIAL PROTOCOL (HRP-580)

PROTOCOL TITLE: App-Assisted Day Reconstruction to Reduce Treatment Burden and Logistic Toxicity in Cancer Patients – Aim 1

VERSION DATE: 01/05/2023

been deployed in a wide range of research studies across the U.S. to collect daily activity engagement and well-being data, and Dynamica developed a HIPAA-compliant version of the app that is currently being trialed in two medical research studies at the University of Minnesota, including “Using smartphone sensor technology to characterize ambulatory patterns of patients with peripheral artery disease receiving supervised exercise training”, and “Implementing Personalized Exercise Prescriptions through Mobile Health in Rural Elderly Cancer Survivors”.[27-30]

2.3 Existing Literature: The relevant literature is cited in sections 2.1 and 2.2 above. There is an urgent need for a tool that generates accurate, comprehensive, and timely measures of logistic toxicity.

## 3.0 Study Endpoints/Events/Outcomes

3.1 Primary Endpoint/Event/Outcome:

Interviews: Identify themes to develop 1) a cancer-specific, multi-tiered activity/trip classification system to organize cancer treatment-related activities and trips in the app; and 2) user stories to describe what the users want to do with the proposed app.

Follow-up survey: Overall satisfaction with proposed system design will be measured using a 5-point Likert scale from not at all satisfied to very satisfied. The primary endpoint will be the proportion of participants who report an overall satisfaction score of 4.0 or above.

## 4.0 Study Intervention(s)/Interaction(s)

4.1 Description: 20 individuals with cancer will be asked to complete 45-minute interviews for input on features that the app should include.

## 5.0 Procedures Involved

5.1 Study Design: Qualitative interviews with follow-up surveys.

5.2 Study Procedures:

**CAB**: All aspects of the proposed work will be conducted with input from a CAB to be led by Drs. [name] and [name]. In quarterly and ad hoc virtual meetings, the CAB will assist in finalizing strategies for major project tasks. CAB engagement will focus on determining the preliminary format and contents of the app-generated logistic toxicity summary reports. To enable patients to solicit help from the cancer care system, the summary reports need to be meaningful and digestible to all CAB members.

**Patient interviews**: We will perform 45-minute interviews via phone or Zoom among 20 English-speaking individuals >18 years old who are currently receiving

## **SOCIAL PROTOCOL (HRP-580)**

**PROTOCOL TITLE:** App-Assisted Day Reconstruction to Reduce Treatment Burden and Logistic Toxicity in Cancer Patients – Aim 1

**VERSION DATE:** 01/05/2023

treatment for cancer. After recruitment and obtaining informed consent, an interviewer trained by Drs. [name] and [name] will use a semi-structured guide including open-ended questions. Following review by the research team and CAB, the interview guide will be assessed after the first five interviews for any necessary changes. If significant edits are made, those interviews will be treated as pilot data and left out of the analysis. Interviews will be digitally recorded and transcribed verbatim.

After the system design, the 20 interview participants will be sent a follow-up survey (approximately 15 minutes) online via REDCap or paper via mail to review the user interface sketches and app function narratives. Participants will be asked to provide open-ended feedback as well as their satisfaction ratings with each user interface sketch and app function narrative using a 5-point Likert scale from not at all satisfied to very satisfied. For each participant, the satisfaction ratings will be averaged to derive an overall satisfaction score.

- 5.3 Follow-Up: Survey data will be collected.
- 5.4 Individually Identifiable Health Information: We will obtain written HIPAA agreement from participants and authorization to communicate via email if that is the participant's preference.

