## 11.0 Number of Participants

11.1 Number of Participants to be Consented: up to 30, 20 participants to complete interviews

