## 17.0 Statistical Considerations

17.1 Data Analysis Plan:

Evaluating the interviews: Two coders will read the patient interview transcripts and identify themes grounded in the transcripts by using a computer-assisted qualitative data analysis system (NVivo) and applying the grounded theory approach and constant comparative method. Major categories in the classification system will be broad enough to remain relevant across contextual examples of logistic toxicity. Each major category will include subcategories to cluster specific activity examples.

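### Does setting aside the first five interviews after a significant change to the guide weaken the qualitative analysis?

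*Combined protocol and SAP*

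**What the plan says.** Section 5.2 (Patient interviews) says the interviewer "will use a semi-structured guide including open-ended questions". The guide is reassessed once five interviews are done, and "If significant edits are made, those interviews will be treated as pilot data and left out of the analysis". Without significant edits, all five stay in. The same section states: "Interviews will be digitally recorded and transcribed verbatim".

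Section 17.1 has two coders derive themes from the transcripts, "applying the grounded theory approach and constant comparative method". Major categories are meant to be broad, and "Each major category will include subcategories to cluster specific activity examples". The interview part of the primary outcome in Section 3.1 is to "Identify themes to develop 1) a cancer-specific, multi-tiered activity/trip classification system", together with user stories.

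On numbers, Section 11.1 gives "up to 30, 20 participants to complete interviews". The Revision History explains the rise in consents from 20 to 30 and adds that the "goal remains the same to obtain interviews from 20 participants". The protocol does not say whether interviews set aside as pilot data are replaced, and it does not define what counts as a significant edit.

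**The concern.** Five patients would each have given about 45 minutes, and their recordings would be on file as transcripts. Open-ended interviews produce no fixed-item score that a change of guide would make impossible to pool, and constant comparison can set early and late transcripts side by side. On that view, leaving five transcripts uncoded discards usable material for the price of a version tag.

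The stake would be completeness. A concrete activity example heard only in the first five interviews would not reach the classification system or the user stories. If the five were not replaced, the analysis would rest on 15 interviews instead of 20, a loss of 5/20 = 25%.

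**Working it through.** **1. The plan's own figure.** The only precision statement is ±18% for the satisfaction rate with 20 participants (Section 17.2). It gives no confidence level or assumed rate. Two ordinary choices reproduce it:

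- 95% confidence, rate 0.80: 1.96 × √(0.80 × 0.20 / 20) = 17.5%
- 90% confidence, rate 0.50: 1.645 × √(0.50 × 0.50 / 20) = 18.4%

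This figure depends on the number of survey respondents, not on the number of coded transcripts. The rule in Section 5.2 leaves interviews out of the analysis and does not say that those five people leave the survey. The ±18% is therefore not affected.

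**2. Inputs for the themes.** From the documents: 5 interviews at risk, a goal of 20, a ceiling of 30 consents. Assumed, because the documents give nothing: the share q of patients who have a given experience; independence between patients; each such patient mentions it if asked under the revised guide; and the yield r of the early guide relative to the revised one.

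**3. Formula.** The chance that the experience appears at least once, with n revised-guide interviews and the five early ones kept, is

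P = 1 − (1 − q)^n × (1 − r·q)^5.

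Setting r = 0 gives the result with the five excluded.

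**4. Results (%).** Cells with three values are for r = 0.25 / 0.5 / 1.

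| q | 15 revised only | 15 revised + 5 early | 20 revised only | 20 revised + 5 early |
|---|---|---|---|---|
| 5% | 53.7 | 56.5 / 59.2 / 64.2 | 64.2 | 66.3 / 68.4 / 72.3 |
| 10% | 79.4 | 81.9 / 84.1 / 87.8 | 87.8 | 89.3 / 90.6 / 92.8 |
| 20% | 96.5 | 97.3 / 97.9 / 98.8 | 98.8 | 99.1 / 99.3 / 99.6 |

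Example, q = 10%, r = 0.5: 1 − 0.9^15 × 0.95^5 = 1 − 0.2059 × 0.7738 = 84.1%. With 20 revised-guide interviews and the five excluded: 1 − 0.9^20 = 87.8%.

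**5. Which columns to compare.** The case for retention compares column 2 with column 3, or column 4 with column 5, as if keeping the five always added five transcripts. That holds only if the number of revised-guide interviews is the same under both rules. With a goal of 20, retained interviews would ordinarily count towards it, so retention leads to column 3. Excluded interviews could be replaced: 20 + 5 = 25 interviews, within 30 consents, which leads to column 4. Column 3 minus column 4, in percentage points from unrounded values:

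| q | r = 0.25 | r = 0.5 | r = 1 |
|---|---|---|---|
| 5% | −7.7 | −5.0 | 0 |
| 10% | −6.0 | −3.8 | 0 |
| 20% | −1.6 | −0.9 | 0 |

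On this comparison retention never wins for r up to 1, and it loses whenever the early guide was less productive. A lower yield is the natural expectation, since the rule applies only when that guide needed significant change.

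**6. The comparisons that favour retention.** If the five would not be replaced, column 3 against column 2 gives gains at q = 10% of 2.4 and 4.7 points for r = 0.25 and 0.5. If the five were kept on top of 20 revised-guide interviews, column 5 against column 4 gives 1.4 and 2.8 points. At q = 20% no gain exceeds 2.4 points, even with r = 1.

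**The case for a change.** The strongest counter-argument is that the protocol does not commit to replacing the five. If recruitment stops at 20 interviews held, exclusion means 15 analysed, and retention then gains a few points for no more than the coding of transcripts already on file. Retention also avoids a decision, taken after the interviews have been held, on whether the edits were significant. And r need not be below 1 for every topic: an early question later dropped may have drawn out examples that the revised guide misses.

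Much of this is true as far as it goes. The silence on replacement is real, and so is the undefined trigger. But silence supports the 15-interview scenario no better than the 20-interview one, and Sections 5.2 and 11.1 both speak of 20 interviews. Retention has its own unsettled judgement: coders would have to decide which themes arise only from new or changed questions, and in open-ended transcripts a version tag does not settle that. That grounded theory can absorb a changing guide is general methodological reasoning; the protocol names the method without saying so. It shows that retention is possible, not that exclusion is worse. Finally, one extra mention of a rare example need not change broad major categories, and the advisory board and the open-ended survey feedback (Section 5.2) are further routes by which such examples can reach the design.

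**Conclusion.** The concern does not hold. Treating early interviews as pilot data after a significant change of guide is a recognised choice, stated in advance with its checkpoint, trigger and consequence. It contradicts nothing else in the protocol, biases no endpoint and leaves the ±18% unchanged.

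Whether keeping the five would do better has no fixed answer. At an assumed 10% share and half yield, retention gains 4.7 points if excluded interviews would not be replaced, and loses 3.8 points if they would be replaced and retained ones count towards the 20. These figures rest on assumed shares, yields and independence, and apply only if significant edits are made, for which the documents give no probability. That is a trade-off on which competent methodologists may differ, and no change to the plan is required.
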